10.2. Sample Size Considerations

The dose-escalation portion of this clinical study will enroll up to 24 patients. Dose escalation will follow the 3+3 rule to establish the MTD. Three planned dose levels are to be used ([Table 1](#)). The minimum number of patients required to establish the MTD is 9 patients. In case there is a dose limiting toxicity at each of the 4 dose levels, each cohort of 3 patients will be expanded to 6 patients, in which case a total of 24 patients will be treated.

After the MTD is achieved, up to 2 cohorts (one including the MTD and one alternate dose or schedule) will be expanded to enroll a total of up to 10 patients in each cohort to further evaluate safety and preliminary utility (potential for clinical efficacy) of ABI-009 in the treatment of PAH.

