Study Objectives	
Objectives
 
This phase 1/1b study will involve dose escalation to determine the maximum tolerated dose (MTD) and safety of 16 weeks of therapy (Dose-finding Safety Part) followed optionally by up to 32 additional weeks of therapy (Extension Part) with ABI-009 IV in patients with PAH who are WHO Functional Class II or III despite best available background therapy. The MTD will be determined on the basis of the results from the safety evaluation.
 
After the MTD is reached in phase 1, there will be up to 2 cohort expansions in phase 1b at the MTD and/or one alternate dose or schedule to determine the recommended phase 2 dose. The expanded cohorts will be such that up to 10 patients for each of the cohorts will be enrolled to obtain additional safety and efficacy data, inclusive of patients from phase 1. The recommended phase 2 dose, which may differ from the MTD, will be determined on the basis of results from safety, efficacy, pharmacologic and correlative studies in this phase 1/1b study.
 
Exploratory Objectives
 
• To evaluate pharmacokinetic information that may be correlated with safety and/or efficacy observations.
Study Endpoints	
Endpoints
 
Primary Endpoints
 
• MTD, dose-limiting toxicities (DLT, defined in 7.2.1), and safety profile of 16 weeks of ABI-009 given IV.

- Safety profile of the up to 48 weeks of treatment

Secondary Endpoints

The following will be measured before treatment at baseline and at week 17 (after 16 weeks of treatment in the Dose-finding Safety Part):

- pulmonary vascular resistance (PVR) by right heart catheterization
- pulmonary artery pressure (PAP)
- pulmonary capillary wedge pressure (PCWP)
- central venous pressure (CVP)

The following will be measured at baseline, 5, 9, 13, and 17 weeks:

[figure not shown]
- Doppler-echocardiographic assessments of right ventricular structure and function
- 6-minute walk distance (6MWD)
- WHO functional class
- Pulmonary function test

The following will be measured at every 8 weeks during the additional 32 weeks of the Extension Part (ie, at week E9, E17, E25, and E33):

- 6MWD
- WHO Functional Class
- Pulmonary function test

Exploratory Endpoints

- Pharmacokinetic (PK) profile and trough level of sirolimus for weekly treatment during the 16 weeks of Dose-finding Safety Part and every other week treatment during the Extension Part

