Study Treatments	
This phase 1/1b study will have a 16-week Dose-finding Safety Part to identify recommended phase 2 dose and evaluate the safety and efficacy profile of weekly ABI-009 (via dose-finding and dose-expansion cohorts), followed by an optional 32-week Extension Part to obtain additional safety and efficacy data on longer term treatment with ABI-009.
 
16 weeks of Dose-finding Safety Part
 
In the dose-finding phase 1 portion of the study, 4 dose levels of ABI-009 will be tested in cohorts of 3 patients each (1, 2.5, 5, and 7.5 mg/m², see Table 1), using the 3+3 dose escalation design. There will be no intra-patient dose escalation allowed. Escalation to the next dose level with a new cohort of 3 patients will occur after no DLT was observed in the first treatment cycle of 4 weeks. If a DLT occurs in a cohort, additional 3 patients will be recruited to the cohort. If no further DLTs occur, then a new cohort of 3 patients at the next higher dose level can be enrolled. If 2/6 patients at dose level 1a experience a DLT, then that cohort will be closed to further enrollment and the study may be

	
terminated. If 2/6 patients at dose levels 2a, 3a, or 4a experience a DLT, then the previous dose level is considered the MTD.
 
It is estimated that a maximum of up to 24 patients will be required to achieve the MTD; however, MTD could be reached with as few as 9 patients. Patients will be allowed to dose reduce by one dose level for reasons of toxicity, with a maximum of 2 dose reductions allowed for a patient. At the lowest dose level, a dose reduction of 25% will be allowed.
										
Table 1: Doses of ABI-009 Given Weekly											
	

Dose Level	1a	2a	3a	4a	

ABI-009 Weekly Dose (mg/m²)	1	2.5	5	7.5	

	Dose Level	1a	2a	3a	4a	ABI-009 Weekly Dose (mg/m²)	1	2.5	5	7.5
Dose Level	1a	2a	3a	4a							
ABI-009 Weekly Dose (mg/m²)	1	2.5	5	7.5							

Note: The original protocol (dated December 10, 2015) included dose levels 1 (10 mg/m²), 2, (20 mg/m²) and 3 (30 mg/m²), and dose level -1 (5 mg/m²).
 
After the MTD is reached, in phase 1b, there may be up to 2 cohort expansions at the MTD and/or one alternate dose or schedule to determine the recommended phase 2 dose.
											
Optional 32-week Extension Part											

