4. STUDY POPULATION

4.1. Number of Patients

In phase 1: Up to 24 patients will be enrolled using the standard 3+3 dose escalation design.

In phase 1b: Additional 4-7 patients in up to 2 expansion cohorts to obtain a total of up to 10 patients at each of the 2 dose levels, MTD and an alternate dose or schedule.

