6.2. Dose-finding Safety Part (up to 16 weeks)

A patient is considered enrolled on study day 1 when the IP, ABI-009, is first administered. ABI-009 is to be administered after all other protocol-specified pre-dose assessments have been performed during each visit that it is required. ABI-009 will be administered weekly for 16 weeks. All weekly visits are allowed to occur in a window of ± 3 days.

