6.4. Pharmacokinetic Study

A PK study of sirolimus will be performed with limited PK sampling on all patients in the dose-finding portion of the study during the first 4 weeks of treatment, assessed via central lab:

- Blood samples will be obtained on day 1 (week 1) and will be taken immediately predose (before infusion), immediately after termination of infusion (end infusion), then at 1 hr, 2 hrs, and 4 hrs post infusion. Thereafter, blood samples will be taken every week immediately predose for the next 3 weeks (weeks 2, 3, and 4) to determine a trough level.

Additional PK samples for sirolimus analysis will be obtained for local lab assessment to help correlate AEs with blood levels during treatment:

- From all treated patient in the 16-week Dose finding Safety Part (including expansion cohort/s): Immediately predose starting at week 2 and continuing for the duration of the study
- From all treated patients in the up to 32 weeks of Extension Part: Immediately predose starting at week E2 and continuing every other week for the duration of the study
- Optional PK samples for consenting patients: During weeks 1 and 3 of the Dose-finding Safety Part at 24, 48, and 72 hours post infusion.

Note that T = 0 is defined as the start of infusion, ie, all sample collection times are relative to the start of infusion. The sample at the end of the infusion is collected immediately after the infusion is stopped. If the duration of infusion is changed, the sample should be collected immediately before termination of the infusion and the time noted.

Whole-blood samples will be collected in EDTA tubes for determination of sirolimus in a central laboratory.

Sample Handling for Central Lab:

- Collect approximately 4 mL blood into vacutainer tubes containing EDTA as the anticoagulant.
- Mix the whole blood gently but thoroughly in the tube immediately after collection.
- Split the sample into two tubes. One tube will be kept as a back-up sample.
- Ensure that both tubes are labeled identically.
- Store the blood samples deep frozen at a temperature between -20 and -80°C.
- The samples will be shipped to a designated laboratory.

Sample Labeling:

The following information should be on each sample:

- Protocol number
- Patient ID
- Nominal sample time point
- Collection clock time and date

A simple regression model will be applied to assess the relationship of the pharmacokinetic parameters with dose.

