10. STATISTICAL CONSIDERATIONS

10.1. Study Endpoints

Primary Endpoints:

MTD, DLTs, and toxicities and safety profile of 16 weeks, as well as safety profile of the up to 48 weeks of ABI-009 given IV, in patients with PAH who are WHO Functional Class II or III despite best available background therapy.

In the dose-finding portion of the study, 4 dose levels of ABI-009 will be tested in cohorts of 3 patients each (1, 2.5, 5, and 7.5 mg/m²), using the 3+3 dose escalation design. There will be no intra-patient dose escalation allowed. Escalation to the next dose level with a new cohort of 3 patients will occur after no DLT was observed in the first treatment cycle of 4 weeks. If a DLT occurs in a cohort, additional 3 patients will be recruited to the cohort. If no further DLTs occur, then a new cohort of 3 patients at the next higher dose level can be enrolled. If 2/6 patients at dose level 1a experience a DLT, then that cohort will be closed to further enrollment and the study may be terminated. If 2/6 patients at dose levels 2a or 3a experience a DLT, then the previous dose level is considered the MTD.

The treated population will be the analysis population for all safety analyses. Adverse events will be coded using the Medical Dictionary for Medical Activities (MedDRA) and grouped by their system organ class and preferred term. Summary tables will include the number and percentage of treatment-emergent and treatment-related AEs, AEs of special interest, SAEs, and incidence of patients experiencing dose modifications, dose delay/dose not given, dose interruptions, and/or premature discontinuation of IP due to an AE.

An external Safety Monitoring Committee (SMC) will assess safety data periodically as needed.

Secondary Endpoint(s):

The following will be measurements will be summarized at baseline and at 17 weeks (after 16 weeks of treatment in the Dose-finding Safety Part):

- pulmonary vascular resistance (PVR) by right heart catheterization
- pulmonary artery pressure (PAP)
- pulmonary capillary wedge pressure (PCWP)
- central venous pressure (CVP)

The following will be measurements will be summarized at baseline, 5, 9, 13, and 17 weeks:

- Doppler-echocardiographic assessments of right ventricular structure and function
- 6-minute walk distance (6MWD)
- WHO functional class
- Pulmonary function test

The following will be measurements will be summarized every 8 weeks of the Extension Part (ie, at week E9, E17, E25, and E33):

- 6MWD

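### No DLT count triggers a safety review once a dose has entered phase 1b expansion

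*Combined protocol and SAP*

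**What the plan says.** The cohort-level DLT rules are in the Synopsis (Study Treatments) and Sections 7.1 and 10.1. Section 10.1 introduces them with "In the dose-finding portion of the study, 4 dose levels of ABI-009 will be tested in cohorts of 3 patients each". One DLT in a cohort adds 3 patients. Two DLTs in 6 close level 1a or, at a higher level, make the previous level the MTD. Escalation is read on the first 4 weeks of treatment.

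The phase 1b text (Synopsis; Sections 2.1, 3.1, 4.1 and 10.2) gives cohort sizes only. Section 10.2 states that "up to 2 cohorts (one including the MTD and one alternate dose or schedule) will be expanded", and Section 4.1 gives "Additional 4-7 patients in up to 2 expansion cohorts to obtain a total of up to 10 patients". The Synopsis makes clear that the 10 are "inclusive of patients from phase 1". None of these places gives a DLT count, a pause or a step for revisiting the MTD.

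Section 7.2 has stopping rules in its title, but its content is the DLT definition and individual holds, reductions and restarts. On committee oversight, Section 10.1 says: "An external Safety Monitoring Committee (SMC) will assess safety data periodically as needed".

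The alternate schedule has no interval, dose or visit plan. The Synopsis describes "weekly ABI-009 (via dose-finding and dose-expansion cohorts" as the treatment under study, Section 6.2 says "ABI-009 will be administered weekly for 16 weeks", and Section 7.1 also gives weekly dosing for the 16-week part.

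**The concern.** The 10 patients in an expansion cohort include those from phase 1, so they form one group at one dose. That group is held to a numerical DLT standard in its first 3 or 6 patients and to none afterwards. A level can become the MTD on 0/3 or 1/6, which is little information: the exact 95% upper limits for the DLT rate are 0.71 and 0.64. Three more patients on a 0/3 level could bring it to 2/6, the result that would have rejected it in escalation, and accrual could continue without any required look. From either start the cohort could finish at 4/10 or worse.

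At stake is the exposure of a few further patients to a dose that the plan's own standard would question. MTD, DLTs and safety are the primary endpoints.

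**Working it through.** **Inputs from the plan.** Cohort cap 10; 3 or 6 phase 1 patients at a cleared level; rejection count 2/6; 4-week window for escalation decisions. The plan states no true DLT rate *p*, so 20%, 33% and 40% are assumed. Patients are treated as independent with the same *p*.

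**The plan's own figure.** 10 − 6 = 4 and 10 − 3 = 7 reproduce the stated 4-7 additional patients, read per cohort. The starting points for expansion are therefore 1/6 and 0/3.

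**Chance of finishing at 4/10 or worse under the plan**

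- From 1/6: P(3 or more DLTs in 4) = 4p³(1−p) + p⁴.
- From 0/3: P(4 or more DLTs in 7), binomial.

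| Assumed *p* | from 1/6 | from 0/3 |
|---|---|---|
| 20% | 0.027 | 0.033 |
| 33% | 0.111 | 0.173 |
| 40% | 0.179 | 0.290 |

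**Chance that the proposed pause fires** (second DLT among the first 6, or third among the first 9)

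From 1/6, two DLTs are needed in patients 7 to 9. The pause falls at patient 8 with probability p² and at patient 9 with probability 2p²(1−p).

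- 20%: 0.040 + 0.064 = 0.104
- 40%: 0.160 + 0.192 = 0.352

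From 0/3, the probabilities are:

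- patient 5: p²
- patient 6: 2p²(1−p)
- patient 8: 3p(1−p)² × p²
- patient 9: 3p(1−p)² × 2p²(1−p) + (1−p)³ × p³

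These give:

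- 20%: 0.040 + 0.064 + 0.015 + 0.029 = 0.148
- 40%: 0.160 + 0.192 + 0.069 + 0.097 = 0.518

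A cohort cannot reach 4/10 without at least 3 DLTs in its first 9, so a pause always comes first.

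**Enrolments avoided if a pause ends accrual**: the sum of P(pause at patient *n*) × (10 − *n*), with each patient's window closed before the next enrols.

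- 0/3, 20%: 0.040×5 + 0.064×4 + 0.015×2 + 0.029×1 = 0.515
- 0/3, 40%: 0.160×5 + 0.192×4 + 0.069×2 + 0.097×1 = 1.803
- 1/6, 20%: 0.040×2 + 0.064×1 = 0.144
- 1/6, 40%: 0.160×2 + 0.192×1 = 0.512

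If patients enrol in threes, the count is read only at 6 and 9:

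- 0/3: 0.104×4 + 0.044×1 = 0.460 at 20%, and 0.352×4 + 0.166×1 = 1.574 at 40%
- 1/6: 0.104 at 20%, and 0.352 at 40%

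If all enrol at once, nothing is avoided.

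**Weighting by the chance of clearing 3+3.** P(cleared at 0/3) = (1−p)³ and P(cleared at 1/6) = 3p(1−p)² × (1−p)³. These are 0.512 and 0.197 at 20%, 0.296 and 0.132 at 33%, and 0.216 and 0.093 at 40%.

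- Cleared, then 4/10 or worse: at most 0.512×0.033 + 0.197×0.027 = 0.022 at 20%; likewise 0.066 at 33% and 0.079 at 40%.
- Enrolments avoided, fully sequential: at most 0.512×0.515 + 0.197×0.144 = 0.29 at 20%, and 0.216×1.803 + 0.093×0.512 = 0.44 at 40%.

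These are upper bounds, because a level below 7.5 mg/m² becomes the MTD only if the next level also fails.

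**The case against.** **Oversight exists.** A reader might infer that expansion patients are unprotected. The documents do not support that. Individual holds and reductions (Section 7.2.1), SAE reporting within 24 hours (Section 11.3.2), the SMC, and the sponsor's right to terminate (Section 13.5) all apply. The Safety Committee also judges tolerability for each patient who goes on to the Extension Part, although that review misses patients who stop early. What is missing is only a count that makes a review compulsory.

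**The recommended dose would not be chosen blind.** A 4/10 result would be visible when the phase 2 dose is selected, and that dose may differ from the MTD. The harm is therefore extra exposure along the way, not a concealed signal.

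**The alternate schedule.** A reader might infer that patients could start an untested schedule with no entry step, or that such a cohort contradicts the 4-7 additions because it has no phase 1 patients to count. Neither follows. Sites have only weekly dosing instructions, so a new schedule would first need an amendment with IRB approval (Section 13.4). The body text sets 10 as a ceiling, so a cohort of 4 to 7 is allowed. A closing rule for a schedule that does not yet exist would be premature.

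**The alternate dose.** The 4-7 arithmetic and the wording about expanding cohorts already point to a level tested in phase 1. They do not exclude a level rejected at 2/6, which also has 6 patients and would need 4 more.

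**The gain is small, and the decision after a pause is still a judgement.** Both points stand. They limit the weight of the concern, but the fix costs little.

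**Conclusion.** The gap is real and narrow. The plan's DLT counts end with dose finding, and nothing in phase 1b obliges anyone to review at 2/6 or on the way to 4/10. Per cohort, a count-triggered pause would fire with probability 0.10 to 0.15 at a true rate of 20% and 0.35 to 0.52 at 40%, so it separates the two rates to a useful degree. Given entry to expansion, it avoids about 0.1 to 0.5 enrolments at 20% and 0.4 to 1.8 at 40% when patients enrol singly or in threes. After weighting by the chance of clearing 3+3, this is at most 0.29 and 0.44.

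These figures rest on assumed DLT rates, independent patients, DLTs known within 4 weeks, and a pause that ends accrual. They also take the MTD to enter expansion at 0/3 or 1/6, as the text allows. If a 0/3 level were first taken to 6 patients and stayed at 0/6, the pause would fire with probability p³, which is 0.008 at 20% and 0.064 at 40%. Section 1.2.3.8 (starting-dose rationale) was not in the text available and could not be checked. This is a worthwhile, inexpensive improvement and not a flaw that undermines the design.

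**What to change.** In Sections 7.1 and 10.2, with the Synopsis aligned:

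1. In each expansion cohort, pause accrual for SMC review at the second DLT among the first 6 patients or the third among the first 9. Count phase 1 patients at that dose, and count DLTs in the first 4 weeks of treatment. The SMC and the sponsor decide what follows.
2. Report later DLTs to the SMC without an automatic pause. The window has to be written down because the DLT definition in Section 7.2.1 has no time limit and treatment lasts 16 weeks.
3. State that the alternate dose is a level tested in phase 1, at or below the MTD.
4. Delete the schedule alternative, or leave it to a later amendment that defines it, since expansion dosing is otherwise described as weekly.

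The cost is amendment wording and, per cohort, a 10-15% chance of one SMC pause at a true rate of 20%, against 35-52% at 40%. A pause takes time in a study where accrual is slow: Section 3.2 expects another 12 months of enrolment after the 7.5 mg/m² level was added. Items 3 and 4 add no patients and no delay.

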10.3. Pharmacokinetic Analysis

Pharmacokinetic analysis will include all patients in the phase 1 dose escalation who received ABI-009 during the first 4 weeks (central analysis).

An additional (local) PK study will be conducted to obtain trough sirolimus levels throughout the study (both in the first 16-week Dose-finding Safety (weekly samples) and optional 32-week Extension Part (every-2-week samples) from all enrolled patients , as well as a more detailed sirolimus PK from weeks 1 and 3 from patients who consent. The whole blood concentration of sirolimus will be summarized by descriptive statistics as appropriate. A simple regression model will be applied to assess the relationship of the pharmacokinetic parameters with dose and pharmacodynamics and safety.

11. MONITORING, RECORDING AND REPORTING OF ADVERSE EVENTS

11.1. Toxicities of ABI-009

ABI-009 is a formulation of sirolimus. No unexpected toxicities not already known for sirolimus (Rapamune®) or the sirolimus prodrug, temsirolimus (Torisel®), were identified in the nonclinical toxicity studies, or observed in the phase 1 studies for ABI-009.

More details on the known precautions, warnings, and AEs of sirolimus and rapalogs are found in the Rapamune® and Torisel® Package Inserts [46, 53].

An AE is any noxious, unintended, or untoward medical occurrence that may appear or worsen in a patient during the course of a study. It may be a new intercurrent illness, a worsening concomitant illness, an injury, or any concomitant impairment of the patient's health, including laboratory test values (as specified by the criteria below), regardless of etiology. Any worsening (ie, any clinically significant adverse change in the frequency or intensity of a preexisting condition) should be considered an AE. A diagnosis or syndrome should be recorded on the AE page of the eCRF rather than the individual signs or symptoms of the diagnosis or syndrome.

Abuse, withdrawal, sensitivity or toxicity to the IP should be reported as an AE. Overdose, accidental or intentional, whether or not it is associated with an AE should be reported on the overdose CRF. Any sequela of an accidental or intentional overdose of the IP should be reported as an AE on the AE CRF. If the sequela of an overdose is an SAE, then the sequela must be reported on an SAE report form and on the AE CRF. The overdose resulting in the SAE should be identified as the cause of the event on the SAE report form and CRF but should not be reported as an SAE itself.

All patients will be monitored for AEs during the study. Assessments may include monitoring of any or all of the following parameters: the patient's clinical symptoms, laboratory, pathological, radiological or surgical findings, physical examination findings, or other appropriate tests and procedures.

All AEs will be recorded by the investigator from the time the patient signs informed consent until 28 days after the last dose of ABI-009 and those SAEs made known to the investigator at any time thereafter that are suspected of being related to IP. AEs and SAEs will be recorded on the AE page of the eCRF and in the patient's source documents. All SAEs must be reported to Aadi Drug Safety within 24 hours of the investigator's knowledge of the event by facsimile, or other appropriate method, using the SAE Report Form, or approved equivalent form.

The investigator's clinical judgment is used to determine whether a patient is to be removed from treatment due to an AE. The investigator is responsible for ensuring that all AEs observed by the investigator or reported by the patient that occur after the first dose of IP through the EOT Visit are reported using the applicable eCRF (eg, AE Summary CRF).

11.2. Evaluation of Adverse Events

The investigator must assign the following AE attributes:

- AE diagnosis or syndrome(s), if known (if not known, signs or symptoms)
- Dates of onset and resolution (if resolved)
- Severity [and/or toxicity per protocol]
- Assessment of relatedness to the IP
- Assessment of relatedness to protocol-required procedures
- Action taken

The AE toxicity grading scale used will be the NCI CTCAE Version 4.03.

